Protocol for spin off research project- Circulating tumour cells as biomarkers to predict prostate cancer metastasis for treatment stratification of localised cancer

clinical outcome follow- up over a long period is required to confirm the value of this CTC analysis in determining micro- metastasis, i.e. predicting post-RP PSA failure and future metastasis development.

2.2. Aims:

- I. To establish the value of CTC positivity in predicting post-RP treatment failure, including BCR and new lesions detected by cancer imaging.
- II. To establish the value of a combined CTC test (including CTC enumeration and gene expression) in predicting post-RP treatment failure and the time of the development of BCR and new lesions detected by cancer imaging.
- III. To provide a preliminary assessment of the prognostic value of CTC data (positivity and gene expression) in predicting post-RP PCa metastasis development, overall survival and cancer specific survival and the generation of CTC data for future longer-term follow-up.
- IV. To provide evidence and data which can be used to design a future clinical trial of a CTC-based intervention to be used to guide therapeutic choice in the management of high-risk localised PCa.

3. Summary and synopsis

This study will require 10-year patient follow up for analyses of the primary and secondary endpoints to have statistically significant power. Nevertheless, extensive research activities will be mainly conducted in the first 5-years where research funding has been secured. After the first 5-years, further research activity will only include annual patient clinical follow-up, data collection and statistical analysis. A renewal application for further funding will be submitted by the end of the first 5-year funding period. The overall study set up is summarised in **Table 1**.

Table 1. Overall study summary.

Methodology	Single site, double-blinded, prospective, paired cohort study. Participating patients and clinicians involved in treatment or management will be blinded to the CTC results, to avoid influencing standard patient treatment, management, and progression outcomes after RP.

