Each patient will be allocated a unique ID and will be used by the lab research team. This unique ID will be recorded in the tissue bank database for future correlation analysis of the CTC results with clinical follow-up data. Sample processing will be performed in tissue culture hood in the designated lab. The whole blood sample will be processed within 4hrs for CTC analysis after collection. Standard Operating Procedure (SOP) (C-ProMeta-1) that is generated describing sample process and analyses need to be followed. There will be fewer patients for the post-RP than the pre-surgery blood collection based on patient exclusion criteria after RP.

Based on the sample size calculation 200 patients will be recruited for both pre- and post-surgery blood sample collections for CTC analysis, which are expected to be achieved within the first two years of the project.

Patient informed consent (including the permission to conduct remote longer-term follow-up) and blood sample collection will be performed by the CRF or the clinical care team.

All patients will have a PSA test at 3 months after their RP during a routine follow-up at UCLH. A PSA ≥ 0.2 will be recorded as a treatment failure event and PSMA-PET scans will be performed as standard clinical care at the study hospitals to detect small PCa lesions. After 3 months, patients are referred back to their original referring centres. Patients with negative PSA results at three months will be followed up by telephone or online app by the study CRF in order to ascertain whether subsequent PSA tests are positive (PSA ≥ 0.2), indicating BCR, metastasis occurs as detected by cancer imaging including PSMA-PET scan or if they have received salvage treatment with hormones/radiotherapy. In addition, details of long term follow up, such as post-operative PSA results and record of adjuvant therapies, will be sourced from patients' hospital electronic medical records, or requested from their local GP or health centre. All patients will be followed-up until the end of the project for metastasis progression as detected by imaging, PCa-specific death and death from any causes. In addition to data collected within the 5-year funded period, we plan to conduct remote longer-term follow up with fully informed consent from patients at point of enrolment, including:

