- Contacting patients on an annual basis for 10 years so they may report their PSA and relevant further treatments. Methods of contact will be decided upon with PPI and may consist of list of preferred options including phone call by the CRF and/or use of secure electronic means via automated email prompts, secure website or app data entry. [name] is currently collaborating with primary care colleagues to develop a patient support app under a separate funding support.
- Flagging and linkage to the patients' relevant electronic health data using their NHS number and date of birth. Under the Confidentiality Advisory Group (CAG), we will request treatment, imaging and cancer outcome data from NHS Digital based on ONS-HES-DID (Data Imaging Data) and NCRAS data sets.

We would thus be able to plan analyses of the diagnostic accuracy and predictive value of the CTC-based tests in terms of metastases and progression-based outcomes at 7.5 years and 10 years of follow-up. Further longer-term follow-up after the 10-year will be performed by accessing the GP and NHS digital records if required and with further ethical approval.

Patient recruitment, sample collection and follow-up procedure were summarised in Table 2
Table 2. Patient recruitment, sample collection and follow-up procedure

Procedure	Screening/Baseline	Pre-RP	3 months post op	12 month post op	24 month post op	... each year...	120 month post op
-----------	--------------------	--------	------------------	------------------	------------------	------------------	-------------------

Protocol for spin off research project- Circulating tumour cells as biomarkers to predict prostate cancer metastasis for treatment stratification of localised cancer

Eligibility assessment	x						
Informed Consent	x						
Blood Sample collection		x	x				
PSA		x	x	x	x	x	x
Medical record review and online app/phone follow-up (PSA and/or Adjuvant therapies) rates of BCR, metastasis, other progression events and death				x	x	x	x

7. Evaluating the efficiency of CTC positive score and the gene panel in predicting RP treatment failure.

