will be reported alongside the number of these participants with a positive by CTC result, and positive combined CTC result. Metastases-free, PCa-specific and overall survival will be reported during the 5 years study time frame and it is intended to perform a later analysis at 10 years of follow up. Preliminary investigation of the prognostic value of pre-surgery CTC data in terms of predicting survival outcomes will be investigated using Cox regression, with hazard ratios reported with associated 95% CIs. CTC data will be explored alongside other pre-surgery risk factors such as plasma PSA using multivariate analysis. Recurrence events and follow up CTC results will be reported and compared over time. The above analyses will be applied to the CTC gene panel. The gene panel will also be correlated with the pre- and post- RP CTC number changes and cancer progression events.

CTC results will be presented for the whole cohort who provided analysable blood samples and stratified by those included in the above analyses, and those excluded due to reasons such as a positive surgery margin, other evidence of locally remaining disease, and who subsequently have adjuvant ADT or radiotherapy.

8. Ethics

The study is a spin out project of the parent project authorised under RLTB ethics, where the main research tissue bank approval provided by the London City & East Research Ethics Committee.

9. Data handling, storage and record keeping- to describe who and how the data will be handled, which data nodes will be used, where it will be stored and security of the data

The CRF (funded by QMUL, but with contract at UCLH) will be part of the study management group and will act as the contact point between UCLH and QMUL. Under the MTA and data sharing agreement (DSA) between the two institutions and with patient consent, the CRF will collect blood samples during pre-surgery operation and after the surgery during the first PSA follow-up visit at UCLH.

The following clinical data will be collected for each patient by the CRF:

- Histology reports
- Clinical stage
- Prostate Specific Antigen (PAS) (pre- and post-surgery)
- Imaging (MRI, PSMA-PET/CT and bone scan)
- Results and record of adjuvant therapies
- Treatment date and method for post-surgery cancer recurrence

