The data will be obtained using either electronic medical records at UCLH NHS Trust system or will be requested from patient's local GP or health centres. PCa recurrence, metastasis and the starting of new treatment will also be directly collected from the patients by phone or secure online system/app during the post-operation follow-up period by the CRF. Collection of follow up data from GP and NHS digital records will be with approval from the Confidentiality Advisory Group (CAG)

Each patient will be assigned a unique ID, and this ID will be used for identifying the patient. All samples will be anonymised using this ID. Completed consent forms will be handed over to the RLTB for secure storage. Patient identifiable data and the above

Protocol for spin off research project- Circulating tumour cells as biomarkers to predict prostate cancer metastasis for treatment stratification of localised cancer

clinical data will be held securely in a file designated for the study in the RLTB folder in the Barts Cancer Centre server. The file will be maintained and updated by the RLTB data administrator and the CRF. The file will be password protected and only be accessible to authorised staff, inclusive of RLTB manager, study PI, RLTB data administrator and the CRF.

A sample receipt form will be completed by the research team upon receipt of sample to the Barts Cancer Institute. The time of sample receipt to research site, the condition it is received and where they are stored will be recorded separately which will be accessible to research team. Location of sample will be recorded in item tracker for traceability purposes as a separate arm under RLTB storage.

The data generated from this study will include immunofluorescence images of CTCs, RNA expression data of the metastasis associated genes in CTCs and follow-up data of clinical and cancer progression associated to PCa patients. These data will also be securely stored in a designated folder in the BCC IT server with access to PI and his research team. The data will be curated throughout its life-cycle (during the study and before the data is published). Each Hyzip (a CTC multiplex gene expression analysis system at Angle) gene expression value will be recorded in the original data format and saved in the above designated folder in BCC server and will be available for data sharing after the publication.

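### The blind to CTC results is not stated to cover those who collect outcomes, and CTC and follow-up data share a folder while outcomes still accrue

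*Protocol*

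**What the plan says.** Section 3, Table 1 (Methodology) describes the design as "Single site, double-blinded, prospective, paired cohort study". It then names who is blinded: "Participating patients and clinicians involved in treatment or management will be blinded to the CTC results". The stated purpose is "to avoid influencing standard patient treatment, management, and progression outcomes after RP". Collecting and classifying outcomes is not mentioned.

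Outcome collection is given to the CRF:
- Section 6: "Patients with negative PSA results at three months will be followed up by telephone or online app by the study CRF". The same section adds long-term follow-up: "Contacting patients on an annual basis for 10 years so they may report their PSA and relevant further treatments".
- Section 9 introduces its list of clinical data with "The following clinical data will be collected for each patient by the CRF". It also says that recurrence, metastasis and the start of new treatment "will also be directly collected from the patients by phone or secure online system/app during the post-operation follow-up period by the CRF".

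On access, section 9 opens the identifiable clinical file to the tissue bank manager, the PI, the data administrator and the CRF. It then lists CTC images, CTC gene-expression data and clinical follow-up data together, and continues: "These data will also be securely stored in a designated folder in the BCC IT server with access to PI and his research team". One unique ID is used on both the laboratory and the clinical side (sections 6 and 9).

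On timing, the milestone table in section 4 has CTC analysis in years 0 to 3 and follow-up in years 0 to 4.5.

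**The concern.** The primary result is the sensitivity of pre-surgery CTCs for treatment failure at 4.5 years. The study hypothesis is that most if not all men who fail will be CTC positive. If whoever telephones patients, requests GP records or settles doubtful cases knows the CTC result, failures in CTC-positive men may be found more readily than failures in CTC-negative men. Missed false negatives leave the denominator of sensitivity, so the estimate rises towards the hypothesised value. The negative predictive value and the hazard ratios would move in the same favourable direction.

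The exposed steps are:
- how hard records are pursued after month 3;
- imaging lesions that count without a PSA rise;
- the judgement that a raised PSA has persisted without further treatment;
- the removal of men from the analysed set after surgery, for example for other evidence of local residual disease.

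**Working it through.** **1. Does the blind reach the CRF?** Table 1 covers patients and the clinicians who treat or manage them. Section 6 describes the CRF as employed on the research project and names the clinical care team as a separate alternative for taking consent. Section 10 leaves treatment decisions to a clinical team unrelated to the study. On this wording the CRF is study staff, and no sentence blinds that role or the data administrator. Equally, no sentence gives either of them CTC results by name. For the PI, access to both kinds of data is explicit in section 9.

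**2. Do the periods overlap?** CTC results accumulate over years 0 to 3 and outcomes over years 0 to 4.5. All CTC results are due for the last 4.5 − 3 = 1.5 years of outcome collection, and some exist before that.

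**3. The plan's own figure.** Inputs from section 7 (Sample size): sensitivity 95%, precision ±5 points, 95% confidence interval, prevalence 40%, inflation 8.5%.
- Events = 1.96² × 0.95 × 0.05 / 0.05² = 72.99, rounded up to 73.
- Patients = 73 / 0.40 = 182.5, rounded up to 183.
- Inflated = 183 / (1 − 0.085) = 200.

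These reproduce the stated 73, 183 and 200, so the sample size is not in question. At 95% sensitivity, 73 events contain 73 × 0.05 = 3.65, or about 4, false negatives. The estimate therefore rests on very few men: 69/73 = 94.5%, with one false negative missed 69/72 = 95.8%, with two missed 69/71 = 97.2%. Each one is worth about 1.3 points.

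**4. Effect of uneven ascertainment.** Observed sensitivity = TP / (TP + FN × (1 − m)), where m is the share of failures missed in CTC-negative men and none are missed in CTC-positive men. The number of failures is 200 × 0.40 = 80. The protocol gives no value for m; 25% and 50% are assumptions.

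| True sensitivity | TP, FN | m = 25% | m = 50% |
|---|---|---|---|
| 95% (protocol) | 76, 4 | 76/79 = 96.2% | 76/78 = 97.4% |
| 90% | 72, 8 | 72/78 = 92.3% | 72/76 = 94.7% |
| 85% | 68, 12 | 68/77 = 88.3% | 68/74 = 91.9% |
| 80% | 64, 16 | 64/76 = 84.2% | 64/72 = 88.9% |

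The bias is 1.2 to 2.4 points at 95%, 3.3 to 6.9 points at 85% and 4.2 to 8.9 points at 80%. In the 90% row with half the CTC-negative failures missed, the result is 94.7%, close to the hypothesised 95%.

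**The case against.** The strongest reply is that the exposure is narrow and, for the key role, unproven.

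- **Access.** A reader might infer that the CRF sees CTC results. The protocol does not say so. It is silent for the CRF and the data administrator, and the research team with folder access could mean the laboratory group. The CRF holds a hospital contract and could arguably count as a managing clinician. This stands as far as it goes: the accurate statement is that these roles are not stated to be blinded.
- **Coding.** A reader might also infer that the CRF classifies endpoints. Sections 6 and 9 say only that the CRF contacts patients and collects data. This stands too. No one is named as deciding outcomes, so the blind should attach to the task, whoever performs it.
- **Objectivity.** Most failures are expected to be biochemical recurrence at a PSA threshold of 0.2. The 3-month PSA is routine, scans are standard care, treating clinicians are blinded, and the contact schedule is the same for all men. This bounds the bias but leaves record pursuit and the softer elements of the endpoint exposed.
- **Detectability.** It is tempting to say that the bias could never be found afterwards. The linkage to NHS data planned in section 6 covers treatment, imaging and cancer outcomes and would allow a partial check by CTC status, though PSA is not among the items listed.
- **Size.** At the protocol's own 95% sensitivity, even the assumed losses move the estimate by only 1.2 to 2.4 points, inside the planned precision. This is correct. The larger figures need a true sensitivity well below the hypothesis, which is the case that the study must be able to recognise.

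The double-blind label is not false either, since Table 1 says at once which two groups it means.

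**Conclusion.** The point holds as a gap in the conduct rules. Followed as written, the protocol permits outcomes to be collected or judged with the CTC result known. It does not show that this will happen. The documents do not support a reading in which the primary result is already compromised, or in which the 10-year follow-up is invalid because the group-level association will be known by then: knowing an association is not knowing one man's result, and overall survival is hard to bias through ascertainment.

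The size is unknown. With 80 failures and assumed losses of 25 to 50% of failures in CTC-negative men only, the bias is about 1 to 2 points at 95% true sensitivity and at most 7 to 9 points at 80 to 85%, against a planned precision of 5 points. Who is blinded and who holds which data are matters that this protocol itself fixes, so they should be settled here and not left to an analysis plan. It is a cheap improvement.

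**What to change.** - In Table 1, extend the blind to everyone who contacts patients, requests records, or decides outcomes or post-surgery exclusions: the CRF, the data administrator, and the PI for any outcome decision.
- In section 9, store CTC and gene-expression results in a separate restricted folder, apart from the follow-up data.
- State that the statistician links the two by unique ID only after the 4.5-year outcome data are locked.
- For later follow-up, keep individual CTC results from those who collect outcomes, and apply the same contact and linkage procedures to all men. Patient-reported PSA should keep its present standing, because the planned NHS linkage does not list PSA.

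The cost is folder permissions and a short paragraph in Table 1 and section 9. Section 13 already funds a data administrator and a statistician, the latter for the last 3 of the 5 years, which includes the time of the lock. The drawback is that the PI and CRF cannot look at links between CTC results and outcomes before then.

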Study objectives and endpoints	
Objectives are set in the context of high-risk patients diagnosed with localised prostate cancer scheduled for robot-assisted RP who have not had neoadjuvant ADT, and are listed below.
 
Primary objectives:
 
To establish the value of CTC positivity in predicting post-RP treatment failure, including BCR and new lesions detected by cancer imaging.
 
To establish the value of a combined CTC test (including CTC enumeration and gene expression) in predicting post-RP treatment failure and the time of the development of BCR and new lesions detected by cancer imaging.
 
Secondary objectives
 
To investigate the potential of CTCs in predicting positive lymph node metastasis, which affects the selection and scale of RP as the initial treatment.
 
To assess potential for convenient non-invasive disease monitoring

Protocol for spin off research project- Circulating tumour cells as biomarkers to predict prostate cancer metastasis for treatment stratification of localised cancer

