	
To provide a preliminary assessment of the prognostic value of CTC data (positivity and gene expression) in predicting post-RP PCa metastasis development, overall survival and cancer specific survival.
 
To provide evidence and data which can be used to design a future clinical trial of a CTC- based intervention to be used to guide therapeutic choice in the management of high-risk localised PCa.
 
To evaluate the longer-term prognostic value of CTC detection and CTC gene expression for metastases and cancer-specific survival.
 
Primary endpoint
 
The primary outcome is post-RP treatment failure during the first 4.5 years of follow up from start of recruitment.
 
Post-RP treatment failure is defined as a PSA $\geq 0.2\text{mg/ml}$ at the routine PSA test 3 months after RP (commonly called 'failure to nadir') and remaining at this level or further increase afterwards without further treatment, or imaging detected appearance of cancer lesions.
 
Cancer lesions detected by imaging without a PSA rise might include neuroendocrine PCa and lesions detected by PSAM-PET. This combined post-RP treatment failure primary endpoint will maximally capture all the clinically significant cancer appearance events.
 
Secondary endpoints
 
BCR during the first 4.5 years of follow up: PSA $\geq 0.2\text{ng/ml}$ at any time post-RP and remaining at this level or further increase afterwards without further treatment.
 
Metastasis (any location)-free survival during the first 4.5 years of follow up. Only 5% of subjects with distant metastasis event (based on traditional imaging technologies) within this time frame (4-6).
 
Metastasis (any location)-free survival at 10 years follow up. to confirm that metastatic event rates have increased among the positives, i.e. a declining rate of "false positives".
 
Deaths from any cause during the first 4.5 years of follow up
 
Overall survival at 10 years of follow up.
 
Prostate cancer specific deaths during the first 4.5 years of follow up. Expected to be 2% or less based on previous studies in the post RP context.
 
Prostate cancer specific survival at 10 years of follow up. Our hypothesis is that most if not all of the patients dying of PCa will be in the CTC positive group.

Target sample size	294

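### Table 1 limits the PSA part of the primary endpoint to the 3-month test, while the objectives, primary analysis and sample size count biochemical recurrence at any time

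*Protocol*

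**What the plan says.** **Table 1 (section 3), primary endpoint.** The window is set first: "The primary outcome is post-RP treatment failure during the first 4.5 years of follow up from start of recruitment". Treatment failure is then a cancer lesion appearing on imaging or, provided no other treatment has been given, a PSA of at least 0.2 (printed in mg/ml) found "at the routine PSA test 3 months after RP (commonly called 'failure to nadir') and remaining at this level or further increase afterwards". The cell adds that this combined "primary endpoint will maximally capture all the clinically significant cancer appearance events".

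**Table 1, secondary endpoints.** BCR is listed separately: PSA of at least 0.2 ng/ml "at any time post-RP and remaining at this level or further increase afterwards without further treatment", over the same 4.5 years.

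**Aims (section 2.2) and primary objectives (Table 1).** The first reads "To establish the value of CTC positivity in predicting post-RP treatment failure, including BCR and new lesions detected by cancer imaging". The second adds the time to BCR and to new lesions.

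**Primary analysis (Table 1, and twice in section 7).** Treatment failure is equated with BCR or progression seen on imaging.

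**Section 7, Definitions and Sample size.** BCR is defined as in the secondary endpoint, at any time after surgery. Most primary events are expected to be BCR, and the study is sized on a BCR prevalence of at least 40% over 4.5 years. For the treatment-failure definition the reader is sent to Table 4, which is not in the text available for this review.

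**Section 6, follow-up.** A PSA of 0.2 or more at 3 months "will be recorded as a treatment failure event". Men who are negative then are followed "in order to ascertain whether subsequent PSA tests are positive", and such later results are labelled BCR.

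**The concern.** The two rules classify the same man differently. Table 1 names one test at one time and places any-time BCR in a separate secondary endpoint, so its wording cannot be stretched to cover a PSA rise after a negative 3-month result. The objectives, analysis and sample size need exactly those later rises.

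Case status is the reference standard here. Sensitivity, which is the primary estimate, and specificity, PPV and NPV all change with the definition applied. Under the Table 1 wording the expected number of events loses its stated basis, and with it the planned precision. Men with circulating tumour cells (CTCs) before surgery and a late PSA-only recurrence would also be counted as false positives. The protocol itself calls specificity important because a positive test might one day be used to withhold curative surgery. If the conflict stands until the data are in, the choice between the rules could be made with CTC results in view.

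**Working it through.** **1. Reproduce the plan's figures.** Inputs from section 7, Sample size: sensitivity 95%, precision ±5 points, 95% confidence interval, prevalence 40%, inflation 8.5%.

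- Events = 1.96² × 0.95 × 0.05 / 0.05² = 72.99, so 73. Prevalence does not enter.
- Patients = 73 / 0.40 = 182.5, so 183.
- Inflated: 183 / (1 − 0.085) = 200 (183 × 1.085 = 198.6, rounded up to the same target).

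The arithmetic is sound. The 40% used to get from 73 to 183 and 200 is stated as a BCR rate over 4.5 years. At 40%, 200 men give 80 events.

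**2. Classify one man under each rule.** PSA below 0.2 at 3 months, sustained PSA of 0.2 or more later inside the window, no lesion on imaging:

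| Source | Status |
|---|---|
| Table 1, primary endpoint | non-failure |
| Objectives; primary analysis; section 7 definitions and sample size | failure |

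Under Table 1 he leaves the sensitivity denominator. If CTC-positive he moves from true to false positive; if CTC-negative, from false to true negative. On the protocol's hypothesis that nearly all who recur are CTC-positive, observed specificity and PPV fall.

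**3. Break-even for the literal Table 1 wording.** 73 / 200 = 36.5%. Three-month PSA failures plus imaging lesions must reach that share. No rate is given for 3-month failure or for imaging lesions overall. The nearest figure is in the secondary endpoints: "Only 5% of subjects with distant metastasis event (based on traditional imaging technologies) within this time frame". If that is taken as 0.05 × 200 = 10 men, the other 73 − 10 = 63 (63 / 200 = 31.5%) would have to be 3-month failures or other lesions, such as those on PSMA-PET.

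**4. Precision at assumed total event rates.** The 10%, 20% and 30% are assumptions; 40% is the plan. Wald half-width = 1.96 × √(0.95 × 0.05 / events), with 200 men. Patients needed for 73 events = 73 / rate, before inflation.

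| Rate | Events | Half-width (points) | Exact 95% interval at 95% observed | Patients for 73 events |
|---|---|---|---|---|
| 10% | 20 | 9.6 | 75.1% to 99.9% | 730 |
| 20% | 40 | 6.8 | 83.1% to 99.4% | 365 |
| 30% | 60 | 5.5 | 86.1% to 99.0% | 244 |
| 40% | 80 | 4.8 | 87.7% to 98.6% | 183 |

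The Wald half-width is the plan's own measure, but in the first three rows 95% plus the half-width exceeds 100%, so the exact (Clopper-Pearson) interval is shown beside it.

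**5. The window.** Recruitment in years 0 to 2 and follow-up to year 4.5 (milestones, section 4) give each man 2.5 to 4.5 years, median 4.5 − 1 = 3.5 with even recruitment. That fits the stated median of roughly 3.5 to 4 years. A 4.5-year time point for every man would need data to year 2 + 4.5 = 6.5, past the funded 5 years.

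**The case against.** The best reply is that nobody would analyse the study by the Table 1 sentence. Section 7 equates failure with BCR or imaging progression and defines BCR in full, so a usable definition exists. Table 1's own claim to capture events as fully as possible points the same way, and Table 4 may carry the intended wording. This stands in part: Table 1 is probably a slip and is not the only definition. It does not remove the conflict. If Table 4 agrees with section 7, Table 1 contradicts both; if it agrees with Table 1, the analysis and sample size have the wrong event. Section 6 also comes close to building the split into event recording, with 3-month results logged as treatment failure and later ones described as BCR.

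A second reply is that late PSA recurrences are reported anyway, through the secondary BCR endpoint and BCR-free survival. That is true, so the information is not lost, but it does not settle case status for the primary estimate.

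A third reply is that imaging lesions carry no 3-month limit, so some late recurrences would still count. This stands: if every late recurrence also had a lesion, nothing would be lost.

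A reader might go further and infer a particular collapse in specificity or PPV. The documents do not support a figure, because the share of failures that Table 1 would miss is not given. Nor is the 5% metastasis figure the rate of the imaging part: it concerns distant metastasis on traditional imaging, while the endpoint also takes in lesions on PSMA-PET.

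**Conclusion.** The contradiction is real, concerns the primary endpoint and must be resolved before analysis. It follows from the wording alone and needs no assumption.

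Its numerical effect is conditional. The 73 events are right under either definition. The 183 and 200 patients are right for BCR at any time or imaging lesions at 40%. Under the literal Table 1 wording, ±5 points in 200 men requires an event rate of 36.5% that the protocol does not support. At assumed rates of 10% to 30%, the approximate half-width is 9.6 to 5.5 points. The direction of the effect on specificity and PPV is downward if late recurrences are mostly CTC-positive, as the protocol expects; its size cannot be determined from the document.

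Two stronger readings should be set aside. One is that the sample size is miscalculated: it reproduces. The other is that the 4.5-year window is a second contradiction. The method-of-analysis phrase about a 4.5-year follow-up time point is loose, but it can be read on the study clock used in Table 1 and in the section 4 milestones. The mg/ml unit is a slip within the same Table 1 sentence, not a separate finding.

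**What to change.** Put one definition of the primary endpoint in Table 1, section 7 and Table 4, matching the primary analysis and sample size: BCR as section 7 defines it (PSA of at least 0.2 ng/ml at any time after surgery, expressly including failure to nadir at 3 months, with its persistence condition) or a cancer lesion on imaging, within the 4.5-year study window. Keep BCR alone as a secondary endpoint.

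In the same edit:

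- correct mg/ml to ng/ml in the Table 1 primary endpoint;
- word the time point in section 7, Method of analysis, as 4.5 years from start of recruitment, to agree with Table 1 and the section 4 milestones.

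The cost is a wording amendment. Section 6 already schedules PSA at 3 months and yearly and collects recurrence and imaging outcomes, and section 9 lists PSA and imaging among the data held. No extra patients, tests or visits are needed, and the 73, 183 and 200 stand unchanged.
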